duration of treatment in INS011-14-030 will be based on the length of time they were enrolled in INS011-15-054 such that total duration of treatment in both studies combined will not exceed approximately 48 weeks. Subjects visit entry into INS011-14-030 will be determined at the discretion of the sponsor and the investigator.

The study will be terminated upon 1 of the following:

- The investigational product is successfully approved for marketing in the US
- Sponsor elects to terminate INS011-14-030.

Treatment with established background AEDs will continue without interruption and changes will be permitted as necessary based on safety concerns or due to changes in seizure control as described in Section 4.3.

As described in Table 1 and Section 5.0, visits will be scheduled at Week 1, Week 2, then monthly for 3 months, and then quarterly thereafter. A Screening Visit will be required for all subjects that do not rollover within 14 days of completing their previous study. All subjects will complete the Final Visit/ Discontinuation Visit regardless of when they stop treatment/complete the study. A Follow-up Visit will occur 2 weeks after the Final Visit/Discontinuation Visit.

At each visit, a record of the incidence and severity of adverse events (AEs), treatment-emergent AEs (TEAEs), and SAEs will be collected and this will serve as a primary outcome criterion for this study. Other safety-related parameters such as 12-lead ECG and hematology, chemistry, and urinary analyses will also be assessed at specified visits. Determination of trough plasma levels of cannabidiol and its 7-OH metabolite will be performed at each visit except Visits 3 and 4 (Week 1 and Week 2). This will support safety monitoring and establish the extent of variability during long-term treatment with the investigational product. For subjects taking clobazam, levels of clobazam and its major metabolite (norclobazam) will be measured if there are safety concerns. Seizure diaries will be reviewed to assess control of seizures (frequency, duration, and severity) throughout the duration of the study.

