3.3 Schedule of Events

The Schedule of Events may be found in Table 1.

Subjects should rollover from the previous study as soon as possible following completion of Day 11 activities (INS011-14-029) or when appropriate for INS011-15-054 to avoid interruption of the investigational product. A Screening Visit may be required for all subjects that do not rollover within 14 days of completing their previous study. The duration of each subject's treatment will be determined by the duration of treatment the subject received in their previous study as described in Section 3.1.

Visits will occur weekly for two weeks, monthly for 3 months, and then quarterly thereafter. A Screening Period (Visit 1) may be required for all subjects that do not rollover within 14 days of completing their previous study. All subjects will complete a Final Visit/Discontinuation Visit regardless of when they stop treatment/complete the study. Discontinuation may occur due to reasons discussed in Sections 3.1 and 3.4.3. A Follow-up Visit will occur 2 weeks after the Final Visit/Discontinuation Visit.

Table 1 Schedule of Events

Assessments ^a	Visit 1 (14 Day Screening Period ^b)	Treatment Period						Final Visit / Discontinuation Visit ^d (Visit 10) Week 48 ±10 days ^e (if not conducted at a normally scheduled visit)	Follow-up Visit Two weeks after Final Visit / Discontinuation Visit (Visit 11) ±5 days
		Visit 2 (Day 1 ^c)	Visit 3 (Week 1) ±3 days	Visit 4 (Week 2) ±3 days	Visits 5, 6, & 7 Monthly: (Weeks 4, 8 & 12) ±7 days	Visits 8, 9, Quarterly: (Weeks 24 and 36) ±10 days ^d			
Obtain informed consent ^f	X	X							
Demographics	X	X							
Review of inclusion/exclusion criteria	X	X							
Medical and surgical history	X	X							
Assessment of current AEDs	X	X	X	X	X	X		X	X
Concomitant medications and procedures	X	X	X	X	X	X		X	
ECG	X	X						X	
Vital signs ^g	X	X	X	X	X	X		X	X
Laboratory values (hematology, chemistry) ^h	X	X				X		X	X
Urinalysis ⁱ	X	X				X		X	X
Pregnancy test ^j	X	X				X		X	X

Assessments ^a	Visit 1 (14 Day Screening Period ^b)	Treatment Period						Final Visit / Discontinuation Visit ^d (Visit 10) Week 48 ±10 days ^e (if not conducted at a normally scheduled visit)	Follow-up Visit Two weeks after Final Visit / Discontinuation Visit (Visit 11) ±5 days
		Visit 2 (Day 1 ^c)	Visit 3 (Week 1) ±3 days	Visit 4 (Week 2) ±3 days	Visits 5, 6, & 7 Monthly: (Weeks 4, 8 & 12) ±7 days	Visits 8, 9, Quarterly: (Weeks 24 and 36) ±10 days ^d			

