3.4.2 Exclusion Criteria

Subjects will not be entered in the study for any of the following reasons:

1. Experienced an anoxic episode related to study drug requiring resuscitation during their previous study.
2. Evidence of other clinically significant disease such as unstable hepatic, hematological, renal, cardiovascular, gastrointestinal, immunological, or pulmonary diseases or ongoing malignancies.
3. Compromised respiratory function or severe respiratory insufficiency.
4. Clinically significant abnormal laboratory values within the past 14 days, including:
 - LFTs such as albumin, direct bilirubin, total bilirubin, aspartate aminotransferase (AST), and alanine aminotransferase (ALT) ≥ 3 times the upper limit of normal (ULN).
 - The investigator may deem the subject eligible if in the opinion of the investigator, the clinically significant abnormal laboratory values are deemed to be acceptable and to not have an impact on subject safety.
5. Inadequate supervision by parent(s)/caregiver(s).
6. For appropriate subjects, an affirmative answer to queries regarding active suicidal ideation with some intent to act but without a specific plan or active suicidal ideation with specific plan and intent on the C-SSRS assessment at the Screening Visit. Subjects who have significant findings for suicidal ideation as assessed by the C-SSRS must be referred to the Investigator for follow-up evaluation.

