3.4.3 Subject Withdrawal

All subjects are free to withdraw from participation in the study at any time, for any reason, specified or unspecified, and without prejudice to further treatment.

The criteria for enrollment are to be followed explicitly. If a subject who does not meet enrollment criteria is inadvertently enrolled, that subject should be withdrawn from the study and the Sponsor must be contacted. An exception may be granted in rare circumstances where there is a compelling safety reason to allow the subject to continue. In these rare cases, the Investigator must obtain documented approval from the Sponsor to allow the subject to continue in the study.

In addition, subjects will be withdrawn from the study in the following circumstances (i.e., stopping criteria):

- The Investigator decides that the subject should be withdrawn for safety
 - If the decision to remove the subject from the study is made because of an intolerable AE or a clinically significant laboratory value associated with the use of the investigational product, the investigational product is to be discontinued, appropriate measures taken, and the Sponsor notified immediately.
- Subject is unwilling to continue in the study and/or the subject or caregiver withdraw consent
- Lack of compliance with protocol
- Investigator or Sponsor stops the study for any reason
- Subject becomes pregnant
- Laboratory values demonstrate a subject serum ALT or AST level >3 times ULN (requires confirmation within 2 days)
- Laboratory values demonstrate a subject serum total bilirubin in excess of >2 times the ULN (requires confirmation within 2 days)
- Subject is enrolled in error
- Subject is lost to follow-up.
 - Lost to follow-up will be defined as a subject failing to attend planned study visits or to response to contacts by the study center staff contacts after

documented 2 attempts and for whom no other contact information is available.

Subjects who discontinue the study early will be asked to complete the Final Visit/Discontinuation Visit, with assessments to be completed as indicated in Table 1.

Subjects may elect to withdraw from study treatment with the possibility of completing remaining visits to allow for monitoring until end of study. All data taken through the subject withdrawing consent or the Investigator or Sponsor decision to discontinue the study, as well as data from the Final Visit/ Discontinuation Visit, will be collected for discontinued subjects.

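### Table 1 schedules no liver chemistry between Day 1 and Week 24 while Section 5.2.3 orders it at Weeks 4 and 8, and the entry rule for liver values does not match the stopping rule

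*Protocol*

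**What the plan says.** **Stopping rules.** Section 3.4.3 states that "subjects will be withdrawn from the study in the following circumstances (i.e., stopping criteria"). The list includes "Laboratory values demonstrate a subject serum ALT or AST level >3 times ULN (requires confirmation within 2 days") and "Laboratory values demonstrate a subject serum total bilirubin in excess of >2 times the ULN (requires confirmation within 2 days"). The same section allows a sponsor-approved exception, "An exception may be granted in rare circumstances where there is a compelling safety reason to allow the subject to continue", but only for a subject enrolled inadvertently without meeting the criteria.

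**Test schedule.** Section 6.1.4 lists ALT, AST and bilirubin under serum chemistry, says liver tests will be watched closely, and refers to Table 1 for timing. The Table 1 row "Laboratory values (hematology, chemistry") is marked at Visits 1, 2, 8, 9, 10 and 11 and is blank at Visits 3 to 7. Section 5.2.3 lists a hematology and chemistry draw among the procedures for Visits 5 and 6. Section 5.2.4 (Visit 7, Week 12) lists none. Section 3.1 relies on both sources at once: "As described in Table 1 and Section 5.0, visits will be scheduled at Week 1, Week 2".

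**Entry rule.** Exclusion 4 (Section 3.4.2) bars clinically significant abnormal laboratory values, including liver tests at or above 3 times ULN. It then adds: "The investigator may deem the subject eligible if in the opinion of the investigator" the values are acceptable and do not affect safety. No ceiling is given.

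**The concern.** A laboratory stopping rule works only if the test is drawn. Between Day 1 and Week 24 the investigator may raise the dose to 40 mg/kg/day (Sections 4.1 and 4.1.1) and may start, stop or adjust antiepileptic drugs (Section 4.3). Section 6.1.1.1 names a rise in liver enzymes as an event to look for. If one site follows Table 1 and another follows Section 5.2.3, the chance of detecting a stopping value depends on which page the site reads. Long-term safety is the primary objective and there is no data monitoring committee (SAP 4.1), so the scheduled tests carry much of the surveillance.

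The entry rule raises a second problem. A child admitted under the override with ALT or AST above 3 times ULN already meets a withdrawal criterion once the value is confirmed. One section lets the child in and another requires the child's removal.

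**Working it through.** The plan states no figure for the interval between tests, so there is none to reproduce.

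**Is the blank real?** Read against the same column headers, the vital-signs row of Table 1 is marked at Visits 3, 4 and 5–7, and the plasma-level row at Visits 5–7. The columns line up, so the blank laboratory cells are not an artefact of text extraction.

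**Inputs.** Day 1 is study day 1. Week 8 is day 56 (window 49 to 63) and Week 24 is day 168 (window 158 to 178); SAP Table A gives the same days. Table 1 footnote h lets results up to 14 days before first dose serve as Visit 2. Maximum enrolment is 60 from INS011-14-029 and 20 from INS011-15-054 (Section 8.1).

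**Longest interval without a scheduled panel**

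| Source | Nominal | Within visit windows |
|---|---|---|
| Table 1, Day 1 to Week 24 | 168 − 1 = 167 days | 158 − 1 = 157 to 178 − 1 = 177 days |
| Table 1, Visit 2 results carried over by 14 days | 167 + 14 = 181 days | up to 177 + 14 = 191 days |
| Section 5.2.3, Week 8 to Week 24 | 168 − 56 = 112 days | 158 − 63 = 95 to 178 − 49 = 129 days |

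Against 48 weeks (48 × 7 = 336 days), 167/336 = 49.7%.

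**Scheduled panels after Day 1 through Visit 10, for a subject followed for all 48 weeks.** Table 1: Weeks 24, 36 and 48, so 3, of which 0 fall before Week 24. Section 5.2.3: Weeks 4, 8, 24, 36 and 48, so 5, of which 2 fall before Week 24.

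**Difference in workload.** 60 × 2 = 120 panels for INS011-14-029 subjects. If all 20 INS011-15-054 subjects also attended Weeks 4 and 8, 80 × 2 = 160.

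**Entry rule against stopping rule**

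| Value at entry | Exclusion 4 | Section 3.4.3, once confirmed |
|---|---|---|
| ALT or AST exactly 3 × ULN | excluded unless overridden | continue |
| ALT or AST > 3 × ULN | excluded unless overridden, no ceiling | withdraw |
| Total bilirubin > 2 and < 3 × ULN | under the numeric limit | withdraw |
| Total bilirubin ≥ 3 × ULN | excluded unless overridden, no ceiling | withdraw |

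The last three rows can conflict. Section 6.1.4 adds that a subject with confirmed clinical significance is either not included or, if already enrolled, followed until the value normalizes. That sentence mentions neither the override nor mandatory withdrawal, so it does not settle which rule governs.

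**The case against.** The strongest reply is that this is a clerical mismatch. Section 5.2.3 is an instruction to sites, and a blank table cell does not forbid a test that the text orders. Investigators may add tests, a medical and safety data review runs throughout (Section 3.2), and the sponsor receives periodic safety listings (SAP 4.2). The Laboratory Manual, not available here, may resolve the timing.

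Part of this stands. The protocol does order early liver tests, so a reader who infers that none is planned before Week 24 goes too far. The long interval arises only at a site that works from Table 1. But Section 6.1.4 sends sites to Table 1 for laboratory timing, and listings can show only tests that were drawn. Discretionary testing lessens the gap without closing it.

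On entry, one may say that medical stability (inclusion 3) and the exclusion of unstable hepatic disease (exclusion 2) keep out most such children, and that an investigator can judge bilirubin below 3 times ULN clinically significant and exclude it. Both points narrow the affected group. Neither reconciles the two rules.

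Three further inferences are tempting and are not supported:

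- *The PK SAP sets a third laboratory schedule.* Its design section describes panels at all visits but one, but it still names INS011-14-024, INS011-14-025 and adult subjects. It appears to be carried over from an older design, and it does not instruct sites.
- *Week 4 and Week 8 panels have no clear place in the by-visit tables.* SAP 6.3 presents data recorded at the nominal visit, so a panel drawn at Visit 5 is reported at Visit 5.
- *Off-schedule liver values are lost to the analysis.* SAP 6.3 lets unscheduled values count toward worst-case summaries where required. The table templates, not available here, would carry the remaining detail.

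**Conclusion.** Two conflicts in the protocol stand.

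The first is the more important: Table 1 and Section 5.2.3 disagree on whether chemistry is drawn at Weeks 4 and 8, and neither is given precedence. Under Table 1 the mandatory liver stopping rules have no scheduled test for 167 days nominal, 177 at the edge of the visit window, or 191 with carried-over Visit 2 results. Under Section 5.2.3 the longest interval is 112 days (95 to 129). These figures assume a subject who starts at Visit 2, as INS011-14-029 subjects do. INS011-15-054 subjects may enter at a later visit, so the interval may not apply to them in full. The figures count scheduled tests only and take no account of the unseen Laboratory Manual.

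The second is that exclusion 4 and Section 3.4.3 conflict for ALT or AST above 3 times ULN admitted under the override, and for total bilirubin above 2 times ULN. The documents do not allow an estimate of how many children this would affect; the number may be small.

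The schedule conflict alone warrants correction, because detection of a mandatory stopping value should not vary by site.

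**What to change.** **1. Schedule.** Make Table 1 show hematology and chemistry at Visits 5 and 6, as Section 5.2.3 does. Visits 5, 6 and 7 share one column, and a plain mark there would also order a Week 12 panel that Section 5.2.4 does not list. Split the column, or add a footnote limiting the mark to Visits 5 and 6. Draw the sample with the plasma-level blood already taken at those visits, so no extra venepuncture is needed. Cost: up to 120 panels (at most 160) at sites now following Table 1, and slightly more blood per draw in small children. The longest scheduled interval becomes 112 days nominal.

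**2. Entry.** State in Section 3.4.2 that no subject may enter with ALT or AST above 3 times ULN or total bilirubin above 2 times ULN, whether or not the override is used. This closes both the missing ceiling and the bilirubin gap, which a cap on the override alone would leave open. Cost: slightly stricter entry.

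Both are protocol clarifications; neither requires a change to the SAP.

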1.1.4.1 Pharmacokinetics

Oral doses of cannabidiol (10 mg/kg/day) once daily for 6 weeks in patients with Huntington's disease results in mean weekly plasma concentrations of 5.9 to 11.2 μ g/L.^{51,52} The mean t_{1/2} for cannabidiol is 24 and 31 hours when administered intravenously (IV) or inhaled, respectively, with a range of 18 to 33 hours.⁵³ Cannabidiol is cleared from plasma at rates between 960 and 1560 mL/min and the distribution volume is estimated to be approximately 30 L/kg.⁵³

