6.1.1 Adverse Events

An Adverse Event (AE) is any untoward medical occurrence in a subject administered a pharmaceutical product. It does not necessarily have a causal relationship with this treatment.

Seizures should not be considered an AE unless they differ significantly from the subjects' baseline. The onset of a new seizure type, as well as an injury incurred as a result of any seizure should be recorded as an AE.

A SAE is any untoward medical occurrence (whether considered to be related to investigational product or not) that at any dose:

- Results in death

- Is life-threatening
 - This requires that the subject be at a risk of death at the time of the event; it does not refer to an event that hypothetically might have caused death if it were more severe.
- Requires inpatient hospitalization or prolongation of existing hospitalization
 - Hospital admissions and/or surgical operations planned before or during a study are not considered AEs if the illness or disease existed before the subject was enrolled in the study, provided that it did not deteriorate in an unexpected way during the study.
- Results in persistent or significant disability/incapacity
- Is a congenital abnormality/birth defect
- Other medically significant events, which do not meet any of the criteria above, but may jeopardize the subject and may require medical or surgical intervention to prevent a serious outcome listed in the definition above (e.g., blood dyscrasias such as anemia requiring blood transfusion).

An adverse drug reaction (ADR) is defined as all noxious and unintended responses to a medicinal product related to any dose. An unexpected ADR is defined as any adverse reaction, the nature of which is not consistent with the applicable product information.

The Investigator is responsible for recording all AEs observed during the study through the Follow-up Visit. Each AE will be evaluated for duration, severity, frequency, seriousness, and causal relationship to the study treatment. Action taken with the study treatment and outcome will also be recorded.

Definitions for severity and causal relationship to the study treatment are presented below.

Severity

The severity of the AE will be characterized as mild, moderate, or severe according to the following definitions:

- Mild events are usually transient and do not interfere with the subject's daily activities.

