8.3.4.1 AEs

The TEAEs are defined as AEs that first occur or worsen in severity after the first administration of the investigational product. Such AEs will be coded using the MedDRA coding dictionary and will be summarized by presenting the number and percentage of subjects having any AE, having an AE in each SOC, and having each individual AE as reported by PT. Furthermore, a summary for SAEs and summaries by severity and relationship to the investigational product will be presented by dose and overall. The most frequent (5%) AEs and drug related AEs will also be provided.

All percentages will be based on the number of subjects in the Safety Population.

In the summaries, AEs will be counted only once per subject. If a subject reports the same AE more than once, it will be counted with its worst severity and closest relationship to investigational product. Only those AEs that begin between start and end of study will be summarized.

The AEs will also be listed by subject and dose.

Subject death due to any cause and subjects with AEs leading to investigational product discontinuation will be listed and summarized by dose and overall.

The proportion of subjects that discontinue investigational product or experience dose interruption due to treatment emergent AEs will be summarized by dose and for all subjects.

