13. PRIOR AND CONCOMITANT MEDICATIONS

Prior and concomitant medications, as collected on the *Concomitant Medication* eCRF page, will be summarized for the SAF, by age category and overall. They will be presented by PT and coded using the latest version of the World Health Organization Drug Dictionary (WHO-DD).

See [Appendix 1](#) for handling of partial dates for medications. In the case where it is not possible to define a medication as prior, concomitant, or post treatment, the medication will be classified by the worst case (i.e. concomitant).

- ‘Prior’ medications are medications which started and stopped prior to the first dose of study medication.
- ‘Concomitant’ medications are medications which:
 - started prior to, on or after the first dose of study medication and started no later than 6 days following end of study medication,
 - AND ended on or after the date of first dose of study medication or were ongoing at the end of the study.
- ‘Post’ medications are medications which started more than 6 days following the last dose of study medication.

Prior and concomitant medications observed during the Follow-up period will also be summarized by CBD status.

Prior and concomitant medications will also be listed.

In addition, AED medication(s), including stopping or starting medication(s), may be adjusted throughout the trial to maximize seizure control based on tolerability as judged by the investigator. AEDs are recorded on the *Concomitant Medication* eCRF page where the “Reason for medication” is ticked “Antiepileptic drug (AED)”.

Changes in AED medication(s) will be analyzed as follows:

- The number of different AEDs a subject took during the study will be summarized
- A bar chart will present the mean number of seizures versus the number of unique AEDs taken during the study for each age category and overall and by type of seizures (separate graphs for tonic and atonic seizures).
- AEDs will be flagged in the listing for all prior and concomitant medications

As for overall concomitant medications, incidence of AEDs will be summarized for each PTs by age category and overall.

AEDs observed during the Follow-up period will also be summarized by CBD status.

Document: C:\Users\q832483\Documents\Insys CSR\Pending\Ready for QC\New folder\Statistical Analysis Plan.docx
Author: [REDACTED] Version Number: V1.0 Final
Version Date: 04APR2017

Template No: CS_TP_BS016 – Revision 3
Effective Date: 01May2012

Reference: CS_WI_BS005

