17.1. ADVERSE EVENTS

Adverse Events (AEs) will be coded using the latest version of MedDRA central coding dictionary.

Treatment emergent adverse events (TEAEs) are defined as AEs that first occur or worsen in severity after the first administration of the study medication.

See [Appendix 1](#) for handling of partial dates for AEs. In the case where it is not possible to define an AE as treatment emergent or not, the AE will be classified by the worst case; i.e. treatment emergent.

An overall summary of number of subjects within each of the categories described in the sub-section below, will be provided as specified in the templates. In the summaries, AEs will be counted only once per subject. Only those AEs that begin between start and end of study will be summarized.

Each summary described in Adverse Event section (except [Section 17.1.2](#) and [Section 17.1.3](#)) will be repeated for TEAEs observed during the Follow-up period and presented by CBD status.

Listings will include TEAEs and Non-TEAEs.

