APPENDIX 1. PARTIAL DATE CONVENTIONS

Imputed dates will NOT be presented in the listings.

ALGORITHM FOR TREATMENT EMERGENCE OF ADVERSE EVENTS:

START DATE	STOP DATE	ACTION
Known	Known	If start date < study med start date, then not TEAE If start date >= study med start date, then TEAE
	Partial	If start date < study med start date, then not TEAE If start date >= study med start date, then TEAE
	Missing	If start date < study med start date, then not TEAE If start date >= study med start date, then TEAE
Partial, but known components show that it cannot be on or after study med start date	Known	Not TEAE
	Partial	Not TEAE
	Missing	Not TEAE
Partial, could be on or after study med start date	Known	If stop date < study med start date, then not TEAE If stop date >= study med start date, then TEAE
	Partial	Impute stop date as latest possible date (i.e. last day of month if day unknown or 31st December if day and month are unknown), then: If stop date < study med start date, then not TEAE If stop date >= study med start date, then TEAE
	Missing	Assumed TEAE
Missing	Known	If stop date < study med start date, then not TEAE If stop date >= study med start date, then TEAE

Document: C:\Users\q832483\Documents\Insy CSR\Pending\Ready for QC\New folder\Statistical Analysis Plan.docx
Author: [REDACTED] Version Number: V1.0 Final
Version Date: 04APR2017

Template No: CS_TP_BS016 – Revision 3
Effective Date: 01May2012

Reference: CS_WI_BS005

STATISTICAL ANALYSIS PLAN: PROTOCOL INS011-14-030

Page 37 of 40

START DATE	STOP DATE	ACTION
	Partial	Impute stop date as latest possible date (i.e. last day of month if day unknown or 31st December if day and month are unknown), then: If stop date < study med start date, then not TEAE If stop date >= study med start date, then TEAE
	Missing	Assumed TEAE

ALGORITHM FOR PRIOR / CONCOMITANT MEDICATIONS:

START DATE	STOP DATE	ACTION
Known	Known	If stop date < study med start date, assign as prior If stop date >= study med start date and start date <= end of treatment, assign as concomitant If stop date >= study med start date and start date > end of treatment, assign as post study

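### The TEAE rule is bounded by first dose and end of study but not by last dose, and no planned summary separates events that start off drug before the Final Visit

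*Protocol*

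**What the plan says.** The definition is the same in both documents. Protocol 8.3.4.1: "The TEAEs are defined as AEs that first occur or worsen in severity after the first administration of the investigational product". SAP 17.1: "Treatment emergent adverse events (TEAEs) are defined as AEs that first occur or worsen in severity after the first administration of the study medication". The SAP Appendix 1 algorithm applies it by comparing AE dates with the study-medication start date only: "If start date >= study med start date, then TEAE". End of treatment is not tested for AEs.

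The one upper limit is in SAP 17.1 (also in Protocol 8.3.4.1): "Only those AEs that begin between start and end of study will be summarized". Collection runs just as long (Protocol 6.1.1): "The Investigator is responsible for recording all AEs observed during the study through the Follow-up Visit".

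Time off drug within the study is foreseen. Protocol 3.4.3 says: "Subjects may elect to withdraw from study treatment with the possibility of completing remaining visits to allow for monitoring until end of study". SAP 9 counts discontinuation from treatment separately from discontinuation from study.

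The SAP does use a last-dose limit elsewhere. Under SAP 13 a concomitant medication is one that, among other conditions, "started no later than 6 days following end of study medication"; later starts are classed as post-treatment. SAP 12 treats procedures in a similar way.

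SAP 7.4 and 17.1 repeat most AE summaries by CBD status, but only for the period from Final Visit to Follow-up Visit.

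**The concern.** TEAE incidence is the primary criterion of this long-term safety study. A reader will take the main TEAE tables to describe what happens on cannabidiol. If some subjects stop early and keep attending, those tables also hold background events and events following withdrawal of drug, under the same label and over the same Safety Population denominator. Relative to an on-treatment count, off-drug onsets can only add events.

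The terms at stake matter. SAP Appendix 2 lists seizure and status epilepticus as events of special interest. A worsening of seizures months after the drug was stopped would appear as a treatment-emergent event of special interest. By-visit results have the same gap: SAP 6.3 summarises them by nominal visit, with no mark for visits held off drug.

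**Working it through.** The plan states no figure for this point, so there is none to reproduce. The check has three parts.

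**1. Length of the off-drug window.** Inputs: Final Visit at Week 48 and Follow-up Visit two weeks later, nominally Week 50 (Protocol Table 1). For a subject who takes the last dose at Week w and attends to the end:

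- days before the Final Visit = (48 − w) × 7
- days to the Follow-up Visit = (50 − w) × 7

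| Last dose | To Final Visit | To Follow-up Visit |
|---|---|---|
| Week 4 | 308 | 322 |
| Week 12 | 252 | 266 |
| Week 24 | 168 | 182 |
| Week 36 | 84 | 98 |

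Visit windows can add up to 10 + 5 = 15 days. The middle column falls outside any planned split by CBD status.

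**2. Comparison with plausible carry-over.** Protocol 1.1.4.1 gives a half-life "with a range of 18 to 33 hours". Five half-lives is 5 × 18/24 = 3.75 days to 5 × 33/24 = 6.9 days. These values are for intravenous or inhaled drug, and no oral value is given there, so they are a guide only. For the Week 12 stopper, a 6-day carry-over leaves 266 − 6 = 260 days off treatment. The 30-day post-dose AE reporting window of Protocol 6.1.3 leaves 266 − 30 = 236. The choice of carry-over hardly alters the picture for an early stopper.

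**3. Effect on reported incidence.** The documents give neither the number of subjects who stop and stay nor a background rate, so both are assumed. For a term with constant weekly rate r, the chance of at least one event by Week t is 1 − exp(−r × t). For a subject who stops at Week 12 and stays to Week 48:

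| r per week | By Week 12 | By Week 48 | Difference |
|---|---|---|---|
| 0.5% | 0.058 | 0.213 | 0.155 |
| 1% | 0.113 | 0.381 | 0.268 |
| 2% | 0.213 | 0.617 | 0.404 |

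The change in overall incidence is the difference times the share of subjects who stop at Week 12 and stay:

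- 5% of subjects: 0.05 × 0.155 = 0.8 points; 0.05 × 0.268 = 1.3; 0.05 × 0.404 = 2.0
- 20% of subjects: 0.20 × 0.155 = 3.1 points; 0.20 × 0.268 = 5.4; 0.20 × 0.404 = 8.1

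In person-time, with the maximum of 80 subjects followed for 48 weeks (3,840 person-weeks) and no other dropout, the off-drug share before the Final Visit runs from 4 × 24/3,840 = 2.5% (4 subjects stopping at Week 24) to 16 × 44/3,840 = 18% (16 subjects stopping at Week 4).

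**The case against.** The strongest reply is that the long off-drug state may hardly arise. It rests on one optional sentence in Protocol 3.4.3. Protocol 3.1, a footnote to Table 1 and SAP 3.1 call for a Final/Discontinuation Visit whenever a subject stops treatment or completes the study, with follow-up two weeks later. If that visit is held at treatment stop, the off-drug tail is about two weeks and the CBD-status tables already show it. This reading is available, but it does not fit the option to complete the remaining visits, and the documents do not settle the conflict. Even on this reading, post-dose events stay in the main tables.

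A reader might also infer four stronger things that the documents do not support.

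- *That counting never ends.* It ends at end of study.
- *That off-drug events cannot be separated.* SAP 6.1 puts Study Day in the listings and SAP 14 lists first and last dose dates, so dated events can be sorted by hand. What is missing is a planned summary.
- *That incidence rises from 11% to 38%.* Those figures describe one hypothetical subject at an assumed rate. Moreover, 38% is what a completer has at the same rate, so a retained subject is observed as long as a completer and is not inflated relative to one.
- *That the TEAE window should simply close 6 days after last dose.* A hard cut would remove about 14 − 6 = 8 days of the Follow-up period from the TEAE tables planned for it. It could label as post-treatment the events of subjects who continue CBD after the Final Visit. It would also pass over the 30-day window in Protocol 6.1.3. The 6-day rule is itself not uniform: the Appendix 1 medication algorithm uses end of treatment with no added days.

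It is also true that the study is descriptive and single-arm, that inclusive counting does not hide a signal, and that no exposure-adjusted rates are planned, so ending exposure at last dose (SAP 14.1) distorts no planned calculation. These points support keeping the all-study tables. They do not remove the need to show which events began on drug.

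**Conclusion.** The point holds as a gap in the planned summaries. Adverse events starting well after last dose but before the Final Visit would be tabulated as treatment-emergent, and no planned table separates them. CBD status does not help for that period; it contrasts subjects who continue CBD after the Final Visit with those who stop then, and a subject who stopped at Week 12 fits neither group cleanly.

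The effect on overall incidence is likely to be small: about 1.3 points for a term with a 1% weekly background rate if 5% of subjects stop at Week 12 and stay, and 5.4 points if 20% do. Across the rates tried, the range is 0.8 to 8.1 points. This rests on an assumed constant rate, an assumed share of stoppers, and the reading of Protocol 3.4.3 that allows long off-drug attendance. If no subject stops and stays, this pre-Final-Visit effect is nil.

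**What to change.** 1. Keep the all-study TEAE tables and the Follow-up tables by CBD status as planned.
2. In SAP 17.1 and Appendix 1, add an on-/off-treatment flag for each AE. Base it on the last CBD dose from any source, including CBD continued after the Final Visit or under Expanded Access, plus a pre-specified carry-over period. The SAP's 6 days could be the main choice and the protocol's 30 days a sensitivity analysis; the choice should be justified.
3. Present the TEAE, SAE, special-interest and death summaries split by that flag.
4. Flag by-visit results obtained off drug.
5. Reconcile the Final Visit text in Protocol 3.1, Table 1 and SAP 3.1 with the option in Protocol 3.4.3 to complete remaining visits, so that it is clear how long off-drug observation can last.

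The cost is one derived flag and one extra set of tables. The SAP already takes the last study-medication date from the eCRF, and SAP 3.1 has the date of entry to Expanded Access recorded there, so no new data should be needed. The downside is that some late drug effects will appear in the off-treatment column, where they remain visible.
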